Those who decide to participate will be asked to attend a baseline visit prior to beginning their exercise programme to determine if they are suitable. The research project will be re-explained and questions encouraged. Following this, informed consent will be obtained if appropriate. A clause outlining the conduction of an interview, voice recording and use of anonymous quotes will be included in the consent form, but this will be optional. Patients will still be able to participate in the study without completing an interview.

Baseline and follow-up visits

Baseline and follow-up visits will be completed for all research participants who complete the full intervention timeframe (i.e. 6-8 weeks). Those choosing to discontinue the intervention before completing the full intervention timeframe will be withdrawn. Follow-up visits will be completed immediately following completion of the HIIT programme, and then 12-weeks post-intervention. An additional follow-up will also be completed 4-weeks post-intervention at the Hull site only.

[figure not shown]
Travel expenses for study visits (baseline and follow-ups) will be reimbursed. Patients can be reimbursed a maximum of £75 to cover the costs of transport/parking that may be accrued.

Patients will be asked not to eat a heavy meal or smoke for 3 hours before the visit and testing (18). Patients will also be asked to dress appropriately, especially in terms of footwear and instructed to avoid unusual physical activity efforts in the preceding 12 hours (18). As testing will not be performed for diagnostic purposes, patients will not be asked to withdraw or refrain from taking any medications (18). At each study visit, the patient's medical notes will be reviewed before assessment of current and past medical history. Patients will be asked questions relating to previous medical history including previous

diagnoses, current symptoms, and medications to determine the presence of any contraindications to exercise testing (18, 19).

Resting blood pressure and HR will then be taken followed by height, weight, body mass index (BMI), waist circumference, hip circumference and waist to hip ratio. During the baseline and subsequent visits, a number of objective physiological and subjective patient-level measures will be performed.

Trial Procedures

Measurement of primary and secondary endpoints

Primary endpoint – safety, utility and tolerability

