Safety will be determined by the occurrence of any adverse events (AE) or serious adverse events (SAE). In accordance with the GCP decision tree for adverse event reporting all events will be reported to the sponsor and recorded to determine the safety of the intervention.

Utility will include eligibility (n = eligible/screened), recruitment (recruited/eligible), and adherence (number of patients completing the HIIT programme). The number of patients screened, recruited and commencing the HIIT programmes will be monitored at each hospital site. A register (if required, i.e. more than one patient attending), will be taken at each exercise class to record patient adherence and the completeness of each session will be recorded (i.e. how many minutes the patient completed). It is estimated that all patients should complete 18 sessions in total within 6 weeks. However, where any sessions are missed, the intervention period can be extended to 8 weeks to allow these sessions to be added on. Those not completing 18 sessions over the extended 8-week period will be deemed to have satisfactorily completed the intervention as long as they have completed >80% of the intervention (i.e. ≥ 15 out of 18 sessions). All patients completing the allotted 6-8 weeks for the intervention (regardless of whether they have completed \geq or < 15 sessions) will still be followed up. Those choosing to discontinue the intervention before completing the full intervention timeframe will be withdrawn.

Tolerability will be assessed by identifying if patients are able to reach and maintain the prescribed training range required to perform HIIT, for each full interval. Heart rate (HR) data will be collected throughout each HIIT session and saved on an encrypted USB stick this will then be compared to the 85-100%HRMax training range that has been prescribed – to determine if patients are able to achieve it. This range will be in line with an ongoing HIIT trial in CAD at 85-90% peak power output (PPO), aiming to achieve >85%HRMax, derived from CPET (15). If patients are not able to achieve 85-100%, this will determine the suitability of this HIIT protocol in this population. Reasons for stopping the HIIT exercise sessions (e.g. leg pain), will be recorded.

Secondary endpoints

Acceptability

Acceptability will be assessed by patient feedback using semi-structured interviews.

conducted using a sample of patients in three groups:

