The HIIT intervention will be performed by using a cycle ergometer with exercise prescription based on the workload achieved during a cycle CPET. The use of a treadmill may preclude patients from reaching their prescribed HIIT training zones due to the onset of claudication whilst a cycle may reduce the risk of falls in very deconditioned patients (34). It has been demonstrated that the limiting symptoms during treadmill walking were often experienced in the leg, mainly the calf, whereas the limiting symptoms during cycling were much more varied (34). Furthermore, one study, albeit small, noted that cycle testing was better tolerated than treadmill testing, which is important considering that the HIIT training zone requires the patient to exercise to near-maximal levels, similar to during a CPET (35).

Inclusion criteria:

- Community dwelling adults aged 18 or over.
- ABPI <0.9 at rest or a drop of more than 20mmHg after exercise testing
- Ability to walk unaided
- English speaking and able to comply with exercise instructions

Exclusion criteria:

- Patients who are unable to provide informed consent
- Critical limb ischaemia/rest pain
- Active cancer treatment
- Significant comorbidities precluding participation in exercise testing and/or training as per the American College of Sports Medicine Guidelines (19).
- Resting/uncontrolled tachycardia (>100bpm) and/or Resting/uncontrolled hypertension (SBP >180mmHg or DBP >100mmHg)
- Symptomatic hypotension

Additional exclusion criteria

Further to analysis of CPET results, patients will be prevented from continuing their involvement in the study if there is indication of:

- Exercise-induced ischaemia or significant haemodynamic compromise.

N.B. – Patients who are able to perform a maximal effort CPET according to previously published guidelines (19) will undergo the intervention which will be prescribed on the basis of their initial CPET. This will be referred to as maximal HIIT.

Patients unable to perform a maximal effort CPET, will still undergo the intervention which will be prescribed on the basis of their initial CPET values, but will be referred to as submaximal HIIT.

Subject recruitment

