Patients who are deemed appropriate for referral to SEP as is usual practice will be informed of the research study evaluating HIIT as a novel exercise intervention for IC. Patients will then be sent a patient information sheet, detailing the aims and details of the study and what the intervention entails. Patients will then be contacted via telephone at least a week later to discuss their interest to undertake the intervention. Those who choose to participate in the study will be asked to attend for baseline assessment. Those who do not choose to partake in the research will be offered the usual SEP, without research. Those also declining the usual SEP will be referred back to their consultant.

Withdrawal of subjects

Participants are free to withdraw at any time and do not have to give a reason for doing so. If a participant exhibits any of the exclusion criteria or loses capacity to consent after enrolment on the study, they will be withdrawn. Full details of any withdrawal will be recorded in the case report form and withdrawal can occur at any time, including during the intervention or follow-up.

Trial exit

Patients will exit the trial if:

- They have completed their intervention and all follow-up assessments.
- They request or are unable to continue intervention or follow-up
- They suffer an adverse or serious adverse event meaning they are no longer able to continue
- They lose the capacity to consent
- They die.

General information**Potential patient benefits**

SEPs have proven to be effective for improving walking distance in patients with IC but are not always feasible or available (11, 14, 36). Other exercise interventions may provide a similar benefit and allow access for a greater number of patients. HIIT has demonstrated beneficial effects in the cardiac population (33, 37), which may be transferrable to the IC population, due to the similar disease aetiology. Therefore, patients may benefit from having a greater range of exercise options that may provide similar benefits, allowing them

to choose their preferred option, thus increasing availability and potentially uptake and adherence.

Potential risks/barriers to the patient

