Data obtained from all participants will be included in the data analysis and no data will be excluded on the basis of intervention and follow-up adherence. Therefore, all collected data at each time point will be analysed.

Baseline characteristics will be summarised descriptively using mean (\pm SD) for normally

distributed data and using median and range for non-normally distributed data. Categorical variables will be presented as frequency and percentages.

Rates of uptake, completion, dropout, adverse or serious adverse events and missing outcome data will be summarised and participation in the intervention will be described as the mean number of sessions attended and the mean time to completion (in weeks) to allow for comparison between actual and theoretical total intervention time.

In addition, tolerability will be assessed by comparing the mean heart rate achieved during each HIIT session to the 85-100% maximum heart rate range calculated from CPET.

Secondary endpoints such as changes in MWD, PFWD, VO_{2Peak} , VAT, ABPI and QoL at each time-point will be assessed using a repeated-measures general linear model.

All quantitative analyses will be conducted using the SPSS statistics software at the conventional two-sided 5% significance level with results presented as mean difference with 95% confidence intervals, associated *p* values and effect sizes where appropriate. Sub-group analysis will also be conducted comparing those who are able to give maximal effort during baseline CPET (and therefore able to perform maximal HIIT) and those who are not (therefore performing submaximal HIIT). Maximal effort will be based on previously published criteria (19, 38). Further sub-group analysis will also be performed comparing those who satisfactorily completed the intervention (i.e. completed $\geq 15/18$ sessions) and those who did not, presuming they do not withdraw from the intervention.

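### A newly met exclusion criterion removes the patient from the study rather than from exercise alone, so follow-up that needs no exertion is lost

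*Combined protocol and SAP*

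**What the plan says.** Withdrawal of subjects sets a mandatory rule: "If a participant exhibits any of the exclusion criteria or loses capacity to consent after enrolment on the study, they will be withdrawn". It adds that "withdrawal can occur at any time, including during the intervention or follow-up".

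Several of the exclusion criteria can arise after enrolment. They include "Critical limb ischaemia/rest pain", active cancer treatment, a resting heart rate above 100 bpm, systolic pressure above 180 or diastolic above 100 mmHg, and symptomatic hypotension. The visit procedures would detect some of them: under Baseline and follow-up visits, notes are reviewed, patients are questioned about contraindications to exercise testing, and "Resting blood pressure and HR will then be taken". Separately, Additional exclusion criteria ends a patient's involvement in the study if CPET shows exercise-induced ischaemia or significant haemodynamic compromise.

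The general schedule is wider. Baseline and follow-up visits says: "Baseline and follow-up visits will be completed for all research participants who complete the full intervention timeframe". Under the primary endpoint, "All patients completing the allotted 6-8 weeks for the intervention" are to be followed up whatever number of sessions they attended. Trial exit does not name a new exclusion criterion, but it does list: "They request or are unable to continue intervention or follow-up".

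On analysis, Descriptive statistics and statistical analysis says that "all collected data at each time point will be analysed", and rules out imputation. Adverse-event reporting runs to 30 days after the final study visit, a term that is not defined.

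**The concern.** Stopping exertion in these patients is right. The CPET is taken to exhaustion and the treadmill walk continues until pain forces a stop. The difficulty is that the rule does more than that. For someone who has finished HIIT, only follow-up remains to be withdrawn from, so the natural meaning of the rule is that the patient leaves the study.

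SF-36, VascuQol, resting ABPI and the adverse-event enquiry need no exercise. Losing them matters for two reasons.

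- **Selection.** Where the trigger reflects deterioration, such as rest pain, the missing values are related to outcome. They are not imputed, and with no control group the later results would rest more on patients who stayed well.
- **Safety.** Adverse events are a primary outcome, and Potential risks/barriers to the patient says that the safety of HIIT in this population is not known. The protocol asks about health at each visit because patients may not volunteer events that they think are unrelated. A lost visit loses that question.

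**Working it through.** **The text, read together.**

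1. Withdrawal is mandatory once any exclusion criterion is met, and it covers follow-up.
2. The meaning of withdrawal is not defined. Two places suggest that it means leaving the study: Baseline and follow-up visits sets completers, who are followed up, against those who stop early, who are withdrawn; and Additional exclusion criteria speaks of involvement in the study as a whole. That CPET rule may be meant for baseline, but it is not limited to it, and CPET is repeated at every study visit.
3. No section keeps such a patient in non-exertional or safety follow-up.

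**The plan's own figure.** Recruitment target: 50 (Hull) + 20 (Coventry) = 70, as Sample size states. It is not based on a power calculation.

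**How many patients.** The documents give no trigger rate. Assume a probability p of 1-5% per visit, independent between visits, with all 70 completing. Only a trigger before the 12-week visit costs a later visit. Hull has two such visits (post-intervention and 4 weeks) and Coventry has one.

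- Hull: 50 × (1 − (1 − p)²) = 0.995 at 1%, 4.875 at 5%.
- Coventry: 20 × p = 0.20 at 1%, 1.00 at 5%.
- Total: 1.195 to 5.875 of 70, or 1.7% to 8.4%.
- If 80% complete: 0.96 to 4.70 patients.

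**How many visits.** Visits due after the post-intervention visit: 50 × 2 + 20 × 1 = 120.

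- Hull: 50 × (2p + (1 − p)p) = 1.495 to 7.375 lost.
- Coventry: 20 × p = 0.20 to 1.00 lost.
- Total: 1.695 to 8.375 of 120, or 1.4% to 7.0%.

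**Effect on a 12-week mean.** If a share w is missing and those patients would have changed by D less on average than the rest, the observed mean is too favourable by w × D. With w from 1.7% to 8.4% and D assumed to be 0.5 to 1 SD, this is 0.017 × 0.5 = 0.009 SD to 0.084 × 1 = 0.084 SD. It is an upper illustration, since not every trigger reflects deterioration.

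These counts cover completers only. Patients who meet a criterion during HIIT come under the same rule and are not counted.

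**The case against.** **There is no contradiction.** A reader might infer that the withdrawal rule and the follow-up rules conflict. The documents do not support that. The primary-endpoint sentence is about the number of sessions attended, the visits section is a general schedule, and the withdrawal rule is a specific exception that names follow-up. A patient with new rest pain can also plausibly fall under the Trial exit item on being unable to continue. This objection stands. It does not restore the data, however, because the visits are lost on that reading too.

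**The rule looks deliberate.** The CPET sentence points to a consistent safety policy rather than a slip. That is fair for exertion, but it gives no reason to stop questionnaires, resting ABPI or safety questions.

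**A transient trigger may not end follow-up.** Contraindications are checked at each visit, and the researcher tries to rearrange missed follow-ups. A site might simply rebook a patient after one high reading. Neither provision overrides the mandatory wording, but permanent loss is less certain than the literal text implies.

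**The remedy is partial.** Walking distances, VO2peak, VAT and post-exercise ABPI all need exertion and would stay missing while tests are contraindicated. This stands in full.

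**Little is at stake.** Completers' HIIT exposure is fully observed; the triggering event, the withdrawal and the missing data are recorded and reported; and utility and tolerability results for completers do not change. This also stands, and it limits the weight of the point.

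**Conclusion.** The point holds as a cheap improvement. Applied as written, the rule removes patients from follow-up that they could safely complete, and where the trigger is deterioration the loss is related to outcome. The number is unknown and probably small: about 1-6 of 70 patients if triggers occur at 1-5% per visit, a rate that is assumed and not taken from the documents. What is affected is quality of life, resting ABPI and late safety enquiry in those patients.

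A reader might also infer that about half of the adverse-event window is lost. From baseline, with HIIT starting at once, the window is 42 + 84 + 30 = 156 days to 56 + 84 + 30 = 170 days, so withdrawal at the post-intervention visit would remove 84 days (84/170 = 49% to 84/156 = 54%). That holds only if the final study visit means the last one attended. If it means the scheduled 12-week visit, which End of trial can support, no days are lost. The documents do not settle this, so the figure should not carry weight; the undefined term is the finding. On either reading, the enquiry at missed visits is lost, though events that become known while the window is open are still recorded.

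**What to change.** - Reword Withdrawal of subjects so that a newly met exclusion criterion stops HIIT, exercise testing or both, as appropriate, but does not end study participation while consent and capacity remain.
- Align the CPET sentence in Additional exclusion criteria and the Trial exit list with this.
- For these patients, continue SF-36, VascuQol, resting ABPI and the adverse-event enquiry to the scheduled 12-week visit, with adverse-event reporting to 30 days after it. Resume exercise tests if the contraindication resolves.
- In Reporting period, state that the final study visit means the scheduled 12-week visit.
- Report walking distances, VO2peak, VAT and post-exercise ABPI as missing because testing was contraindicated, where that is the reason.

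The visits, staff and forms already exist, so the main cost is wording and a protocol amendment, which may need ethics committee review. The downsides are some visits with partial data, and later quality-of-life and ABPI values that may reflect new treatment rather than HIIT.

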Primary outcomes measures: Utility, assessed by screening, eligibility, recruitment and adherence rates. Safety, assessed by determining the occurrence of adverse and serious adverse events, and tolerability, assessed by patient ability to achieve and maintain exercise in the appropriate exercise intensity domain.

Secondary outcome measures: Acceptability assessed via semi-structured interview and changes in MWD and PFWD assessed via graded treadmill test, VO_{2Peak} , ventilatory anaerobic threshold (VAT) assessed via CPET, ABPI and QoL.

Primary endpoint

The primary endpoint for this study will be assessing the utility, safety and tolerability of a 6-week HIIT intervention.

Secondary endpoints

Additional endpoints will include acceptability and improvements in MWD, PFWD, VO_{2Peak} , VAT, ABPI and QoL.

Study design**Identification and screening of patients:**

Potential participants will be identified by vascular surgeons / nurses / technologists (as appropriate to each site) in vascular outpatient clinics or multidisciplinary team meetings (as appropriate to each site) at two tertiary vascular centres, Hull Royal Infirmary (Hull, United Kingdom) and University Hospital Coventry and Warwickshire (Coventry, United Kingdom)

and referred to research nurses / research fellows or exercise physiologists (appropriate to each site) for screening..

Patient Selection

Patients will have a confirmed diagnosis of intermittent claudication made by their consultant either clinically or by questionnaire. Diagnosis will be made with an ABPI of <0.9, a drop-in ankle pressure of ≥ 20 mmHg after exercise, or documented significant atherosclerosis on radiological imaging.

Patient consent

Patients will be sent a letter and patient information sheet. This will provide details of the study, the 6-week HIIT programme and the interview. Patients will then be contacted via telephone call at least a week later to ask any questions and decide whether they would like to partake in the study intervention. Those who do not wish to partake in the research will be offered the usual care SEP without research as is usual practice for IC. Those who also decline this will be referred back to their consultant for future management.

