This study will use a pragmatic and flexible HIIT protocol with a higher intensity than that previously used in the IC population (12). The protocol will consist of 3 sessions per week for 6 weeks, with a work to rest ratio of 1:1 (one-minute interval of HIIT interspaced by one-minute interval of low-intensity exercise), completing 10 sets of HIIT with an overall exercise session time of 20 minutes. The intensity will be set at 85-90% PPO (from CPET) during high-intensity, (aiming to achieve 85-100% HRMax), and at 20-25%PPO during low-intensity bouts. The variation from high to low intensity will be achieved by altering the cycle cadence (rpm). This work to rest ratio has been selected as although HIIT is often prescribed in similar clinical populations using 4-minute intervals at 85-95%HRMax (33), a large RCT recently concluded that HIIT at this intensity is hardly feasible, at least not for a full 4-minutes (15). Our personal experience with cardiac patients has demonstrated that patients may exceed their peak heart rate (from CPET) during HIIT sessions. This is also likely to be the case for those with IC, especially those who are unable to achieve a maximal effort CPET. We will adopt a pragmatic approach to this by allowing it to occur but monitoring on a case-by-case basis and will reduce intensity when deemed appropriate. We will also record these occurrences to allow appropriate reporting.

The HIIT sessions will be preceded and followed by a 10-minute warm up and cool down as is standard practice in exercise rehabilitation for older adults with chronic disease. In addition, patients will be monitored for up to 10 minutes following the cool-down to ensure heart rate is returning to near resting values and/or any symptoms have subsided.

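### Tolerability, a primary outcome, is defined interval by interval but analysed as the mean heart rate of a session that is half recovery

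*Combined protocol and SAP*

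**What the plan says.** Four places in the combined protocol and SAP bear on this.

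- **Primary outcomes measures** lists "tolerability, assessed by patient ability to achieve and maintain exercise in the appropriate exercise intensity domain". It does not mention intervals.
- **Primary endpoint – safety, utility and tolerability** (under Trial Procedures) makes this operational as "identifying if patients are able to reach and maintain the prescribed training range required to perform HIIT, for each full interval". Heart rate is to be collected throughout each session and compared with 85-100% HRMax. Failure to achieve that range is to decide whether the protocol suits this population. For adherence, "the completeness of each session will be recorded (i.e. how many minutes the patient completed".
- **Intervention: High intensity interval training (HIIT) programme** sets a 1:1 ratio of one-minute bouts, "completing 10 sets of HIIT with an overall exercise session time of 20 minutes". Warm-up and cool-down fall before and after the session. High bouts are set at 85-90% of peak power output (PPO), "aiming to achieve 85-100% HRMax), and at 20-25%PPO during low-intensity bouts". The same section expects that "patients may exceed their peak heart rate (from CPET) during HIIT sessions" and allows staff to reduce intensity case by case.
- **Descriptive statistics and statistical analysis** holds the only analysis text for tolerability: "comparing the mean heart rate achieved during each HIIT session to the 85-100% maximum heart rate range calculated from CPET".

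**The concern.** The target range applies to the high-intensity minutes, but the planned statistic averages high and low minutes together. As a measure of what happened in the intervals, it is pulled down by time that is meant to be easy. It also reduces a requirement that applies to every interval to one number per session, so missed or unfinished intervals can disappear into the average.

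This is an uncontrolled proof-of-concept study with no formal sample size calculation, so its descriptive primary outcomes are its main product. The documents set no pass/fail threshold for tolerability, and it does not follow that compliant patients will be declared failures. What is at stake is that the reported figure could fall below range for a patient who did what was asked, or within range for one who did not maintain or complete the intervals. That figure would then inform the judgement on suitability.

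**Working it through.** **1. Session composition.** From the Intervention section: 10 × (1 + 1) min = 20 min, which reproduces the stated session time. Low-intensity share = 10/20 = 50%. If the session were taken to include the 10-minute warm-up and 10-minute cool-down, high-intensity time would be 10/40 = 25%.

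**2. Identity, with no physiological model.** Let H and R be the mean % HRMax over the high and the recovery minutes. Session mean S = (H + R)/2, so S ≥ 85 requires R ≥ 170 − H.

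| H (%) | R needed for S ≥ 85% |
|---|---|
| 85 | 85 |
| 90 | 80 |
| 95 | 75 |
| 100 | 70 |

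The documents give no value for R. Over an assumed range of 65% to 85%, a patient at H = 90 has S from (90 + 65)/2 = 77.5% to (90 + 85)/2 = 87.5%. The result turns on recovery heart rate, which is not part of the tolerability definition.

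**3. Errors in both directions (R assumed).**

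- Every bout at 90%, R = 70%: S = (90 + 70)/2 = 80.0%, below range although every interval was in range.
- Five bouts at 97% and five at 80%, R = 85%: H = (5 × 97 + 5 × 80)/10 = 88.5% and S = (88.5 + 85)/2 = 86.75%, in range although five of ten intervals were below 85%.

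**4. Illustrative model.** All heart-rate inputs here are assumptions. Heart rate moves towards rest + (peak − rest) × load with a first-order lag of 20, 40 or 60 s. Load alternates between 87.5% and 22.5% PPO, the midpoints of the two prescribed ranges. Heart rate starts at the low-load level, and any drift is linear over 20 minutes. Three results are listed in order of lag.

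- Rest 70, peak 130 bpm, no drift: session mean 79.2/79.0/78.8% and high-minute mean 85.2/81.2/79.8%. Including recovery lowers the mean by 6.0/2.2/1.0 points. The share of high-intensity time at or above 85% is 62/34/12%.
- Same patient, upward drift of 10 bpm: session mean 83.1/82.9/82.7%.
- Same patient, drift of 20 bpm: session mean 86.9/86.7/86.5%, in range. At lags of 40 and 60 s, 3 of 10 intervals still average below 85%, and about a third of high-intensity time is below 85%.
- Rest 80, peak 115 bpm, no drift: session mean 86.3/86.2/86.0% over all ten intervals. If the patient stops after five, the mean over the minutes completed is 86.3/86.1/85.8%. Missing half the session barely moves the statistic.

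The two patients differ because of the rest-to-peak ratio. With no lag or drift and a mean load of 55% PPO, S ≥ 85% requires x + 0.55(1 − x) ≥ 0.85, so x = rest/peak ≥ 0.30/0.45 = 0.667. The ratios are 70/130 = 0.538 and 80/115 = 0.696. Two patients who follow the same prescription exactly can therefore fall on opposite sides of 85% because of their resting and peak heart rates.

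**The case against.** The strongest reply is that the Intervention section sometimes uses HIIT for the high bouts alone, so the analysis sentence might mean the average over those bouts. The text does not say so. That reading would remove the dilution by recovery but not the masking: five bouts at 97% and five at 80% average 88.5%, in range with half the intervals missed.

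Second, heart-rate lag can matter more than the recovery minutes. This stands. At lags of 40 and 60 s without drift, recovery costs only 2.2 and 1.0 points, and the high-minute mean is itself below 85% for a fully compliant patient. The 3-of-10 count comes from the first three intervals, and at 40 s the third lies almost exactly at 85%. An interval-level analysis will not put every compliant patient in range, which is why reaching and maintaining should be reported separately.

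Third, the plan describes and classifies no one, the heart-rate trace is saved, and minutes completed and reasons for stopping are recorded. It is true that no rule is stated. But the analysis section plans no summary of minutes completed, and an interval summary chosen after the data are seen would be post hoc.

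Three smaller points also stand. The per-interval wording is in the Trial Procedures definition, not in the outcome list. The resolution of the heart-rate recordings is not stated. Intervals in which staff lowered the intensity need explicit handling.

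**Conclusion.** The concern holds. As written, the analysis of a primary outcome does not measure that outcome as the protocol defines it, and this should be corrected before the heart-rate data are analysed. The conclusion rests on the text and on step 1 of the working: the target applies to the high minutes, half the session is recovery, and the definition requires each interval to be judged. It does not depend on the model.

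The size of the error for a given patient cannot be fixed from the documents. In the assumed 70/130 bpm case without drift, including recovery lowers the mean by 1.0 to 6.0 points. In other assumed cases the session mean is in range while intervals are missed or half the session is not done. The direction depends on resting and peak heart rate, lag and drift, none of which is given.

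**What to change.** Replace the tolerability sentence in Descriptive statistics and statistical analysis with wording that follows the Trial Procedures definition, for example:

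> Tolerability will be analysed per high-intensity interval from the heart rate recorded in each session, leaving out low-intensity minutes, warm-up and cool-down. For each patient, with the 10 prescribed intervals of every attended session as denominator, we will report (a) the proportion in which at least 85% HRMax was reached; (b) how far it was maintained, as interval-mean heart rate (% HRMax) and the share of interval time at or above 85%; and (c) the proportion completed in full. Uncompleted intervals stay in the denominator. Intervals above 100% of CPET HRMax will be reported separately. Results will be summarised across patients.

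Keep both reaching and maintaining; peak heart rate alone would not be enough. Add a line on how intervals with staff-reduced intensity are flagged in these summaries. If the session mean was intended to cover only the high-intensity minutes, say so, and still add the per-interval results.

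The cost is a short text change and some data processing. Heart rate throughout each session and minutes completed are already to be collected. The sponsor should confirm that the recordings are fine enough, and time-marked well enough, to separate one-minute intervals. The exercise prescription does not change.
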